11.3. Efficacy Analyses

Primary Efficacy Outcome

The primary efficacy outcome will be analyzed based on the time from randomization to the first occurrence of symptomatic VTE (lower extremity DVT and non-fatal PE) and VTE-related death (death due to PE or death in which PE cannot be ruled out as the cause) in the ITT analysis set and Up-to-Day-45 analysis phase. The primary statistical alternative hypothesis is that rivaroxaban is superior to placebo on the primary efficacy outcome, that is, time to event for the rivaroxaban group is stochastically later than that for the placebo group from randomization up to Day 45. More specifically, the survival function for the placebo group is lower than that for the rivaroxaban group. The null hypothesis is the negation of the alternative hypothesis, that is, the survival function for the placebo group is not lower than that for the rivaroxaban group. As a further illustration of the hypotheses, for the case where hazard functions are proportional, the above alternative hypothesis can be expressed as that the HR of rivaroxaban versus placebo is less than 1, and the null hypothesis is that the HR is at least 1.

The primary statistical hypothesis will be tested using Cox proportional hazards model, stratified by subjects with CrCl ≥ 30 mL/min and < 50 mL/min versus subjects with CrCl ≥ 50 mL/min, with the treatment (as randomized) as the only covariate. This primary efficacy analysis will be based on the ITT analysis set and Up-to-Day 45 analysis phase. Subjects will be analyzed according to the treatment group to which they are randomized, regardless of actual treatment received. As an operational arrangement, the 2-sided p-value will be reported, and if it is less than the 2-sided alpha of 0.05, then superiority of the study drug will be declared when the observed survival

functions favor rivaroxaban. Note that the above testing procedure is equivalent to stratified logrank test⁴⁰. The use of the Cox model format facilitates a consistent presentation of tests and CIs from analyses of efficacy and safety outcomes and from subgroup and sensitivity analyses.

The point estimate and corresponding 95% CI for the HR (rivaroxaban to placebo) will be provided based on the Cox proportional hazards model. For the CIs, the plausibility of proportional hazards assumption will be assessed by visually comparing the plot of the log of cumulative hazard between treatments, and additionally checked by adding a treatment by logarithm-transformed time interaction into the Cox model. If there is strong indication that the proportional hazards assumption is not valid, the 95% CI for relative risk of rivaroxaban versus placebo based on the incidence of the primary efficacy outcome from randomization up to Day 45 will be additionally provided, using the Cochran–Mantel–Haenszel (CMH) statistic with stratification by CrCl groups.

The cumulative event rate derived from the Kaplan-Meier method will be displayed graphically to evaluate the treatment effect over time.

The following sensitivity analyses of the primary efficacy outcome will be conducted to assess the robustness of the conclusion from primary efficacy analysis: a) stratified Cox model as in the primary efficacy analysis but additionally stratified by region, b) stratified Cox model as in the primary efficacy analysis but based on the per-protocol analysis set and on-treatment analysis phase. Additional post-hoc analyses may be conducted to investigate unexpected results. Off-treatment primary efficacy outcome events will be summarized by treatment groups.

As described in Sections 9 and 10, extensive efforts will be made to collect complete vital status and other outcome data for all subjects randomized in this study. The amount of unavoidable missing follow-up in this study with relatively short treatment duration of 45 days is not expected to influence the conclusion from the efficacy analyses. To illustrate the extent of missingness, the numbers of subjects with missing follow-up and the percentages of missing follow-up time out of supposed follow-up time will be summarized. Sensitivity analyses will be conducted to estimate any additional events from the rivaroxaban and placebo group during the missing follow-up time that are needed to overturn a superiority conclusion from the primary efficacy analysis. Additional details will be provided in the SAP.

Homogeneity of treatment effects, both in HR and direction in the following subgroups will be assessed by subgroup analysis. Analysis methods and any changes to these subgroups will be detailed in the SAP.

- Age (< 65 vs ≥65; <75 vs ≥75 years)
- Sex (men vs women)
- Race (White vs others)
- Geographic region (North America, South America, Western Europe, Eastern Europe, other)
- CrCl (≥30 to <50, ≥50 to <80, ≥80 mL/min)

- Body Mass Index (<25, ≥25 to <35, ≥35 kg/m²)
- Admitting diagnosis (HF with reduced ejection fraction, acute respiratory insufficiency or acute exacerbation of COPD, acute ischemic stroke, acute infectious disease, and inflammatory diseases)
- History of diabetes (yes vs no)
- History of cancer (yes vs no)
- Baseline D-dimer level
- Baseline aspirin use (yes vs no)
- Baseline thienopyridine use (yes vs no)
- Baseline proton pump inhibitor use (yes vs no)
- Duration of index hospitalization (3 to 6, 7 to 10 days)
- Duration of anticoagulation during index hospitalization (3 to 6, 7 to 10 days)
- LMWH or UFH during index hospitalization (LMWH vs UFH)
- Total modified IMPROVE VTE risk factor score (2, 3, ≥4)

Secondary Efficacy Outcomes

Each secondary outcome will be analyzed based on time from randomization to the first occurrence in the ITT analysis set, and the Up-to-Day-45 analysis phase. The same stratified Cox model as that for the primary efficacy outcome will be used. Details will be provided in the SAP.

To control the family-wise type I error rate at alpha of 0.05 (2-sided) in testing for efficacy outcomes, if superiority of rivaroxaban over placebo on the primary efficacy outcome is established, superiority of rivaroxaban over placebo on secondary outcomes will be tested sequentially using a closed testing procedure in the following hierarchical order, each at alpha of 0.05 (2-sided):

- VTE-related death (death due to PE or death in which PE cannot be ruled out as the cause)
- Symptomatic VTE (lower extremity DVT and non-fatal PE)
- The composite of symptomatic VTE and ACM
- The composite of symptomatic VTE (lower extremity DVT and non-fatal PE), MI, non-hemorrhagic stroke and CV death (death due to a known CV cause and death in which a CV cause cannot be ruled out; by this definition, a VTE-related death is considered a CV death)
- ACM

Exploratory Efficacy Outcomes

Each exploratory outcome will be summarized by treatment groups based on the ITT analysis set and Up-to-Day-45 analysis phase.

11.4. Pharmacokinetic Analyses

The population PK model will characterize and predict the overall exposure to rivaroxaban and determine different PK parameters, such as, clearance (CL/F), volume of distribution (V/F), first-order absorption rate constant (Ka), area under the plasma concentration curve (AUC), maximum serum concentration (C_{max}), minimum serum concentration (C_{min}), time to reach maximum concentration in plasma (t_{max}), and half-life ($t_{1/2}$).

A previously developed population PK model will be used in an attempt to externally validate it using data from the current study (ODIXa-DVT, 2006; EINSTEIN-DVT, 2006; BAY 59-7939 /12143, 2008). The model will be utilized to predict the PK parameters for the current medically ill population and to generate empirical Bayesian (individual) predictions for all concentrations in the current data set. Predictive performance check of the model will be analyzed. Changes to the structural components of the model will be performed to address any observed model misspecifications.

11.5. Medical Resource Utilization and Health Economics Analyses

Medical resource utilization and health economics will be descriptively summarized by treatment group.

11.6. Safety Analyses

Bleeding Outcomes

The principal safety outcome will be analyzed based on time from randomization to the first occurrence of ISTH major bleeding. Treatments will be compared using the same Cox proportional hazards model as that for the primary efficacy outcome described earlier. The analysis will be based on the safety analysis set and on-treatment analysis phase. Subjects will be analyzed according to study drug received. If a subject inadvertently receives both drugs, the subject will be analyzed as randomized.

Non-major clinically relevant bleeding and the composite of major plus non-major clinically relevant bleeding will be analyzed based on time from randomization to the first occurrence. The same analysis as that for the principal safety outcome will be used. Bleeding Academic Research Consortium bleeding event classification categories will be analyzed similarly.

All bleeding, other bleeding, as well as sub-categories of major bleeding, including critical sites, will be also summarized by treatment groups.

Adverse Events

For adverse events that are collected as specified in Section 12, ADVERSE EVENT REPORTING, the verbatim terms reported in the eCRF by investigators to identify adverse events will be coded using the most current version of Medical Dictionary for Regulatory Activities (MedDRA). For each MedDRA preferred term, the percentage of subjects who report at least 1 occurrence of the given event will be summarized by treatment group. Additional summaries, listings, or subject narratives may be provided, as appropriate.

Clinical Laboratory Tests

Because this study will not collect laboratory data routinely, laboratory data will not be summarized. Local lab data may be discussed in subject narratives.

Vital Signs

Descriptive statistics of pulse and blood pressure will be provided.

Physical Examination

Descriptive statistics of physical examination findings will be provided.

11.7. Interim Analysis

An interim analysis for futility will be conducted when approximately 50% of subjects with adjudicated primary efficacy outcome events have been observed (about 50% of the expected total number of events based on the actual observed blinded pooled event rate even if this event rate is lower than the assumed rate) and there will be no alpha adjustment to the final analysis. The IDMC will review results of the planned interim analysis and make a recommendation whether the study should be continued as planned, modified, or terminated prematurely due to futility or safety.

The study may be stopped early for futility when it would be unlikely to establish superiority on the primary efficacy outcome and/or a positive benefit over risk of rivaroxaban compared with placebo, if the study were to run to completion. Detailed characteristics of non-binding futility criteria will be specified in the SAP.

11.8. Benefit-Risk Analysis

The benefit-risk of rivaroxaban vs placebo will be evaluated based on the excess number of events between treatments for events intended to be prevented (benefits) and events that may be caused (risks). Excess number of events is defined as the difference in event rate times a hypothetical population size (eg, 10,000 patients). To have a comprehensive benefit-risk evaluation, several comparisons will be considered. One analysis will be based on a comparison between the primary efficacy outcome (the composite of symptomatic VTE (lower extremity DVT and non-fatal PE) and VTE-related death (death due to PE and death in which PE cannot be ruled out as the cause) up to Day 45 post-hospital discharge) and the principal safety outcome (the ISTH major bleeding). This analysis phase includes all data from randomization to Day 45 (inclusive), which is the period of treatment. In addition, benefit-risk balance may be further assessed for secondary efficacy outcomes in relation to major bleeding, while potentially taking into consideration the clinical importance of those events, eg, in the context of irreversible harm. The Kaplan-Meier method will be used to display and evaluate the benefits and risks over time. Also a bivariate approach to benefit-risk assessment will be explored.²¹ Additional details for benefit-risk analysis will be specified in the SAP.

12. ADVERSE EVENT REPORTING

Timely, accurate, and complete reporting and analysis of safety information from clinical studies are crucial for the protection of subjects, investigators, and the sponsor, and are mandated by regulatory agencies worldwide. The sponsor has established Standard Operating Procedures in conformity with regulatory requirements worldwide to ensure appropriate reporting of safety information; all clinical studies conducted by the sponsor or its affiliates will be conducted in accordance with those procedures.

Rivaroxaban has been extensively studied in Phase 1 through Phase 4 clinical studies involving more than 70,000 patients and its overall adverse event profile has been well described. Appropriate information concerning adverse events were systematically collected and submitted to regulatory authorities. For the purposes of this study (and after discussion with appropriate regulatory agencies) a value-driven approach to safety data collection will be utilized. Certain non-serious adverse events will not be collected, while certain events will be collected as suspected outcome events and therefore not reported as serious adverse events. All data on safety and outcomes will be reviewed regularly by an unblinded IDMC.

Section [12.1.1](#) describes the usual definitions of adverse events and serious adverse events.

12.1. Definitions

12.1.1. Adverse Event Definitions and Classifications

Adverse Event

An adverse event is any untoward medical occurrence in a clinical study subject administered a medicinal (investigational or non-investigational) product. An adverse event does not necessarily have a causal relationship with the treatment. An adverse event can therefore be any unfavorable and unintended sign (including an abnormal finding), symptom, or disease temporally associated with the use of a medicinal (investigational or non-investigational) product, whether or not related to that medicinal (investigational or non-investigational) product. (Definition per ICH)

This includes any occurrence that is new in onset or aggravated in severity or frequency from the baseline condition, or abnormal results of diagnostic procedures, including laboratory test abnormalities.

Note: The sponsor collects adverse events starting with the signing of the ICF (refer to Section [12.3.1](#), All Adverse Events, for time of last adverse event recording).

Serious Adverse Event

A serious adverse event based on ICH and EU Guidelines on Pharmacovigilance for Medicinal Products for Human Use is any untoward medical occurrence that at any dose:

- Results in death
- Is life-threatening
(The subject was at risk of death at the time of the event. It does not refer to an event that hypothetically might have caused death if it were more severe.)
- Requires inpatient hospitalization or prolongation of existing hospitalization
- Results in persistent or significant disability/incapacity
- Is a congenital anomaly/birth defect
- Is a suspected transmission of any infectious agent via a medicinal product
- Is Medically Important*

*Medical and scientific judgment should be exercised in deciding whether expedited reporting is also appropriate in other situations, such as important medical events that may not be immediately life threatening or result in death or hospitalization but may jeopardize the subject or may require intervention to prevent one of the other outcomes listed in the definition above. These should usually be considered serious.

For the purposes of this study, efficacy and safety outcomes will not be considered as adverse events or serious adverse events (See Section 12.3.1, All Adverse Events).

Unlisted (Unexpected) Adverse Event/Reference Safety Information

An adverse event is considered unlisted if the nature or severity is not consistent with the applicable product reference safety information. For rivaroxaban, the expectedness of an adverse event will be determined by whether or not it is listed in the Investigator's Brochure¹⁹.

Adverse Event Associated With the Use of the Drug

An adverse event is considered associated with the use of the drug if the attribution is possible, probable, or very likely by the definitions listed in Section 12.1.2.

12.1.2. Attribution Definitions**Not Related**

An adverse event that is not related to the use of the drug.

Doubtful

An adverse event for which an alternative explanation is more likely, eg, concomitant drug(s), concomitant disease(s), or the relationship in time suggests that a causal relationship is unlikely.

Possible

An adverse event that might be due to the use of the drug. An alternative explanation, eg, concomitant drug(s), concomitant disease(s), is inconclusive. The relationship in time is reasonable; therefore, the causal relationship cannot be excluded.

Probable

An adverse event that might be due to the use of the drug. The relationship in time is suggestive (eg, confirmed by dechallenge). An alternative explanation is less likely, eg, concomitant drug(s), concomitant disease(s).

Very Likely

An adverse event that is listed as a possible adverse reaction and cannot be reasonably explained by an alternative explanation, eg, concomitant drug(s), concomitant disease(s). The relationship in time is very suggestive (eg, it is confirmed by dechallenge and rechallenge).

12.1.3. Severity Criteria

An assessment of severity grade will be made using the following general categorical descriptors:

Mild: Awareness of symptoms that are easily tolerated, causing minimal discomfort and not interfering with everyday activities.

Moderate: Sufficient discomfort is present to cause interference with normal activity.

Severe: Extreme distress, causing significant impairment of functioning or incapacitation. Prevents normal everyday activities.

The investigator should use clinical judgment in assessing the severity of events not directly experienced by the subject (eg, laboratory abnormalities).

12.2. Special Reporting Situations

Safety events of interest on a sponsor study drug that may require expedited reporting and/or safety evaluation include, but are not limited to:

- Overdose of a sponsor study drug
- Suspected abuse/misuse of a sponsor study drug
- Inadvertent or accidental exposure to a sponsor study drug
- Any failure of expected pharmacologic action (ie, lack of effect) of a sponsor study drug
- Medication error involving a sponsor product (with or without subject/patient exposure to the sponsor study drug, eg, name confusion)

Special reporting situations should be recorded in the eCRF. Any special reporting situation that meets the criteria of a serious adverse event should be recorded on the serious adverse event page of the eCRF.

12.3. Procedures

12.3.1. All Adverse Events

In this study, recording of only a subset of adverse events is necessary. However, any adverse event of particular concern to the investigator may be recorded in the eCRF to alert the sponsor.

The following are excluded from adverse event collection and reporting, regardless of seriousness or severity. Exempted events will be captured on the eCRF as suspected outcome events only and will be waived from unblinding and exempted from expedited reporting and include:

- VTE-related death (death due to PE or death in which PE cannot be ruled out as the cause)
- MI
- ACS
- Stroke
- TIA
- Symptomatic VTE (lower or upper extremity DVT and PE)
- Bleeding events

If the CEC determines that a suspected event does not meet the criteria for an outcome event as defined in the CEC charter, it will still be excluded from adverse event collection and reporting even if serious criteria were met.

Serious Adverse Events

All serious adverse events that are not outcome events as listed above should be reported to the sponsor as described in Section 12.3.2. While one of the efficacy outcome measures is ACM, any non-VTE-related death will be reported to the sponsor as a serious adverse event.

Certain adverse events are considered to be Adverse Events of Special Interest and should be reported as serious adverse events. These include:

- Suspected severe toxic effect on the bone marrow, such as severe thrombocytopenia (platelet count less than 50,000/ μ L), severe neutropenia (white blood cell count less than 500/ μ L), pancytopenia, aplastic anemia
- Suspected severe hypersensitivity reaction (eg, anaphylaxis, angioedema, severe urticaria, bronchospasm, etc.)
- Severe skin reactions such as Stevens-Johnson Syndrome
- Suspected severe liver injury

Non-Serious Adverse Events

The following should be reported:

- Non-serious adverse events leading to permanent study drug discontinuation
- All severe non-serious adverse events (regardless of relation to study drug) including severe laboratory abnormalities will be collected except the study outcomes.

Any other non-serious adverse events do not require reporting. However, any adverse event of particular concern to the investigator may be recorded in the eCRF to alert the sponsor.

Reporting Timelines and Processes

All adverse events and special reporting situations, whether serious or non-serious, will be reported from the time any signed and dated ICF is obtained until completion of the subject's last study-related procedure (which may include contact for follow-up of safety). Serious adverse events, including those spontaneously reported to the investigator up to the Day 75 (\pm 5d) visit, must be reported using the Serious Adverse Event Form. The sponsor will evaluate any safety information that is spontaneously reported by an investigator beyond the time frame specified in the protocol.

All adverse events, regardless of seriousness, severity, or presumed relationship to study drug, must be recorded using medical terminology in the source document. Whenever possible, diagnoses should be given when signs and symptoms are due to a common etiology (eg, cough, runny nose, sneezing, sore throat, and head congestion should be reported as "upper respiratory infection"). Investigators must record their opinion concerning the relationship of the adverse

event to study therapy. All measures required for adverse event management must be recorded in the source document and reported according to sponsor instructions.

The sponsor assumes responsibility for appropriate reporting of adverse events to the regulatory authorities. The sponsor will also report to the investigator (and the head of the investigational institute where required) all suspected unexpected serious adverse reactions (SUSARs). The investigator (or sponsor where required) must report SUSARs to the appropriate Independent Ethics Committee/Institutional Review Board (IEC/IRB) that approved the protocol unless otherwise required and documented by the IEC/IRB. A SUSAR will be reported to regulatory authorities unblinded. Participating investigators and IEC/IRB will receive a blinded SUSAR summary, unless otherwise specified.

The sponsor assumes responsibility for appropriate reporting of adverse events to the regulatory authorities. The sponsor will also report to the investigator (and the head of the investigational institute where required) all serious adverse events that are unlisted (unexpected) and associated with the use of the study drug. The investigator (or sponsor where required) must report these events to the appropriate Independent Ethics Committee/Institutional Review Board (IEC/IRB) that approved the protocol unless otherwise required and documented by the IEC/IRB.

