9.2.1. Efficacy Evaluations, Outcomes and Adjudication

This is a clinical outcomes study. The primary efficacy outcome is the composite of all symptomatic VTE events (lower extremity DVT and non-fatal PE) and VTE-related death (death due to PE or death in which PE cannot be ruled out as the cause).

Secondary efficacy outcomes are:

- VTE-related death (death due to PE or death in which PE cannot be ruled out as the cause)
- Symptomatic VTE (lower extremity DVT and non-fatal PE)
- The composite of symptomatic VTE (lower extremity DVT and non-fatal PE) and ACM
- The composite of symptomatic VTE (lower extremity DVT and non-fatal PE), MI, non-hemorrhagic stroke and CV death (death due to a known CV cause and death in which a CV cause cannot be ruled out; by this definition, a VTE-related death is considered a CV death)
- ACM

Exploratory efficacy outcomes are:

- Symptomatic lower extremity DVT
- Symptomatic non-fatal PE
- Symptomatic upper extremity DVT
- MI
- Non-hemorrhagic stroke

- Re-hospitalization for symptomatic VTE (lower extremity DVT and non-fatal PE) within 30 days after randomization

Submission of a suspected event for adjudication will be required for:

- All deaths
- Suspected events that include symptoms or signs suggestive of PE or DVT.
- Performance of any imaging or other diagnostic study that could yield an incidental diagnosis of PE or DVT.
- Suspected events that include acute coronary syndrome or MI. Chest pain determined not to be cardiac in origin does not need to be sent for adjudication.
- Suspected events that include symptoms compatible with a TIA or stroke. Events determined not to be a TIA or stroke (eg, seizure, hypoglycemia) do not need to be sent for adjudication.

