Any clinical event that suggests the possibility that an efficacy outcome event has occurred (including ACS and TIA) should be indicated on the Clinical Status page of the eCRF and will be sent for adjudication. Examples of objective testing diagnostic procedures that may have been performed as part of the standard of care are listed in [Attachment 2](#). For imaging studies, a copy of the original study should be sent with the adjudication package. For other tests, a report of the results will suffice. All clinical data must be sent to CEC for adjudication. The CEC may request additional imaging in order to ensure appropriate adjudication. The CEC will apply the definitions (see [Attachment 1](#)) contained in the CEC charter to adjudicate and classify the events while blinded to treatment assignment. Adjudicated results will be used for final analyses.

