9.5. Safety Evaluations and Outcomes

9.5.1. Bleeding Events

The study will include the following evaluations of safety and tolerability according to the time points provided in the [TIME AND EVENTS SCHEDULE](#): ISTH major bleeding, non-major clinically relevant bleeding, other bleeding, adverse events, and clinical laboratory tests.

The study will use the ISTH Bleeding Event Classification Scale to assess bleeding events as major, non-major clinically relevant bleeding, or other bleeding. Similar to efficacy outcomes, the same independent CEC will adjudicate and classify bleeding events according to definitions in the CEC charter. The CEC will also classify bleeding events using the Bleeding Academic Research Consortium scale as a supportive approach.²⁷

The principal safety outcome for this study is major bleeding using validated ISTH bleeding criteria. Other safety outcomes are non-major clinically relevant bleeding and other bleeding.

An ISTH major bleeding event is defined as overt bleeding that is associated with:

- A fall in hemoglobin of 2 g/dL or more, or
- A transfusion of 2 or more units of packed red blood cells or whole blood, or
- A critical site: intracranial, intraspinal, intraocular, pericardial, intra-articular, intramuscular with compartment syndrome, retroperitoneal, or
- A fatal outcome

Non-major clinically relevant bleeding is defined as overt bleeding not meeting the criteria for major bleeding but associated with medical intervention, unscheduled contact (visit or telephone call) with a physician, (temporary) cessation of study treatment, or associated with discomfort for the subject such as pain or impairment of activities of daily life.

Examples of non-major clinically relevant bleeding are:

- Epistaxis if it lasts for more than 5 minutes, if it is repetitive (ie, 2 or more episodes of true bleeding, ie, not spots on a handkerchief, within 24 hours), or leads to an intervention (packing, electrocautery, etc.)
- Gingival bleeding if it occurs spontaneously (ie, unrelated to tooth brushing or eating), or if it lasts for more than 5 minutes
- Hematuria if it is macroscopic, and either spontaneous or lasts for more than 24 hours after instrumentation (eg, catheter placement or surgery) of the urogenital tract
- Macroscopic gastrointestinal hemorrhage: at least 1 episode of melena or hematemesis, if clinically apparent
- Rectal blood loss, if more than a few spots
- Hemoptysis, if more than a few speckles in the sputum, or

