6.2. Adverse Events

For the purposes of this study (and after discussion with appropriate regulatory agencies) a value-driven approach to safety data collection will be utilized. Certain non-serious adverse events will not be collected, while certain events will be collected as outcome and therefore not reported as serious adverse events. All data on safety and outcomes will be reviewed regularly by an unblinded IDMC. For AEs that are collected, the verbatim terms reported in the eCRF by investigators to identify adverse events will be coded using the Medical Dictionary for Regulatory Activities (MedDRA).

Treatment-emergent adverse events (TEAE) are defined as those adverse events that start between the first study drug and the last study drug + 2 days.

Summary of the following adverse events will be provided by treatment group:

- Post-baseline (on or after the first study drug) adverse events
- Treatment-emergent adverse events
- Adverse events with onset > 2 days from the stop of study drug
- Post-baseline serious adverse events
- Treatment-emergent serious adverse events (TESAE)
- Serious adverse events with onset > 2 days from the stop of study drug
- Adverse events leading to permanent study drug discontinuation
- Adverse events with outcome of death

In addition, incidences of some of the above adverse events by system organ class and dictionary-derived (preferred) term will be provided.

Additional summaries, listings, or subject narratives may be provided, as appropriate.

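### Non-fatal ACS without MI, TIA, and serious suspected events the CEC rejects are recorded on the eCRF but reach no planned by-arm table

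*Protocol*

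**What the plan says.** **Exemption.** Protocol 12.3.1 lists VTE-related death, MI, ACS, stroke, TIA, symptomatic VTE and bleeding as outside adverse event collection whatever their seriousness. "Exempted events will be captured on the eCRF as suspected outcome events only". Protocol 12.1.1 sets the general rule that "efficacy and safety outcomes will not be considered as adverse events or serious adverse events", and SAP 6.2 repeats that "certain events will be collected as outcome and therefore not reported as serious adverse events".

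**Rejected events.** If the CEC finds that a suspected event does not meet its outcome criteria, Protocol 12.3.1 says "it will still be excluded from adverse event collection and reporting even if serious criteria were met".

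**Submission.** Protocol 9.2.1 says that a clinical event suggesting that "an efficacy outcome event has occurred (including ACS and TIA) should be indicated on the Clinical Status page of the eCRF" and sent for adjudication. It also requires submission for symptoms or signs suggestive of PE or DVT, and for "Performance of any imaging or other diagnostic study that could yield an incidental diagnosis of PE or DVT".

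**Bleeding.** In Protocol 9.5.1, "An ISTH major bleeding event is defined as overt bleeding that is associated with" one of four listed features. The two lower bleeding classes also require overt bleeding.

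**Deaths.** Protocol 12.3.1 also says that "any non-VTE-related death will be reported to the sponsor as a serious adverse event".

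**Hospitalization.** Protocol 12.3.2 makes any event requiring hospitalization an SAE. It has two exceptions: social reasons, and procedures planned before study entry.

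**The concern.** Exempting outcome events from adverse event reporting is sound when each one is counted as an outcome instead. The difficulty is an event that is exempt, or treated as exempt, and is then not an outcome. It falls between the outcome tables and the adverse event tables.

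This trial compares an anticoagulant with placebo, and the events at issue bear on that comparison: ACS, TIA, and blood loss without a visible source. Whether a rejected event reaches an SAE table may also depend on how the site labelled it, since the same illness can be entered as a suspected outcome or as an adverse event. For hospitalized events and reclassified deaths the protocol gives sites conflicting instructions, so two sites could follow the text and report differently.

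**Working it through.** There is no figure in the plan to reproduce, and no arithmetic applies. The check follows each event type through three questions: is it collected as an adverse event (Protocol 12.1.1, 12.3.1, 12.3.2), is it an outcome (Protocol 3.3.3, 9.2.1, 9.5.1 and Attachment 1; SAP 5.2.1, 5.3.1, 5.5.1 and 6.1), and does an SAP table show it?

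Two SAP rules decide the last question. Efficacy and bleeding analyses use adjudicated outcomes (SAP 2 and 5), and the adverse event summaries cover only adverse events that were collected (SAP 6.2).

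| Event | Adverse event? | Outcome? | In a planned by-arm table? |
|---|---|---|---|
| Non-fatal ACS without MI | Exempt by name | No. Not a CEC class, not in Attachment 1, not in any outcome list | No |
| TIA | Exempt by name | No, for the same reasons | No |
| Other suspected event, serious, rejected by the CEC | Excluded by the rejected-event sentence | No | No, if that sentence is followed literally |
| Hemoglobin fall or transfusion without overt bleeding, submitted as a bleed and rejected | Excluded by the same sentence | No. Every bleeding class needs overt bleeding | No |
| The same, reported as an SAE or severe laboratory abnormality | Collected | No | Yes, SAP 6.2 |
| Non-VTE death to Day 45 | SAE, unless first submitted as VTE-related (two sentences conflict) | Yes, all-cause mortality | Yes, SAP 5.3 |
| Non-VTE death after Day 45 | As above | Outside the Up-to-Day-45 phase | Only in the fatal adverse event table, if reported as an SAE |

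**ACS and TIA.** These drop out without any CEC decision, because they are on the exempt list and in no outcome. Section 9.2.1 does not require submission of chest pain judged non-cardiac or of neurological events judged not to be TIA or stroke. The submitted events are therefore mostly ones the site considered real.

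**Other rejected events.** The rejected-event sentence can be read two ways. Literally, a hospitalization submitted as suspected PE and finally diagnosed as pneumonia stays out of SAE reporting. More narrowly, only the suspected label is dropped, and the final diagnosis is reportable because it is not on the exempt list. The text does not choose, and section 12.3.2 points to the second reading for anything hospitalized. Section 9.2 urges investigators to consider PE in pneumonia, heart failure and COPD exacerbation. These overlap with the index illnesses, so the ambiguity is not remote.

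**Non-overt blood loss.** SAP section 7 lists a hemoglobin drop among the harms without the word overt. It reads as a sub-category of ISTH major bleeding, so it does not clearly close the gap. Laboratory data are not summarized (SAP 6.3).

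**The case against.** The strongest reply is that the data are not lost. Suspected events are on the eCRF, and Attachment 2 refers to dedicated eCRF data for MI/ACS, stroke/TIA and bleeding. Investigators may record any adverse event that concerns them. An unblinded IDMC regularly reviews all safety and outcome data. SAP 6.2 allows further summaries, and SAP section 9 summarizes re-hospitalization and emergency visits by arm. The reduced collection was adopted after discussion with regulators.

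Most of this stands, and it limits the point to planned reporting. It does not remove it. Investigator recording is optional. IDMC review protects subjects during the trial but puts nothing in the final report. The resource summaries are not by these diagnoses, and an allowance for further summaries is not a plan for this one. The documents do not say whether the regulatory discussion covered leaving rejected serious events out of the final tables.

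A reader might infer three stronger things that the documents do not support:

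- **That some non-VTE deaths appear nowhere.** All deaths are adjudicated, and all-cause mortality to Day 45 in the ITT set counts them whatever the assigned cause.
- **That non-overt blood loss is always missed.** It is missed only when submitted as a suspected bleed and rejected. Otherwise it is reportable as an SAE or a severe laboratory abnormality.
- **That every rejected serious event should return to SAE reporting.** That would reopen a deliberate waiver. SUSARs go to authorities unblinded (12.3.1), SAEs carry a 24-hour clock (12.3.2), and a CEC decision comes later. This is a trade-off for the sponsor, not the correction of an error.

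**Conclusion.** The point holds as a gap in planned safety reporting with two internal conflicts. It does not touch the primary efficacy analysis or the principal safety analysis.

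- Followed as written, the plan shows non-fatal ACS without MI and TIA in no by-arm table. The same applies to other serious events submitted as suspected outcomes and rejected, if the rejected-event sentence is read literally.
- Sections 12.3.1 and 12.3.2 disagree on hospitalized events first submitted as suspected outcomes.
- Within 12.3.1, a death submitted as VTE-related and reclassified by the CEC is both an SAE and excluded. This affects the fatal adverse event table, mainly after Day 45.

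The size cannot be given. Neither document states how many events will be submitted or what share the CEC will reject, and under the imaging rule in 9.2.1 many rejected submissions could be negative scans rather than serious events. The conclusion assumes that the separate CEC charter and the SAP's output specifications, which are not part of these documents, do not already provide such a table.

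**What to change.** 1. **SAP 6.2.** Add a by-arm table of suspected outcome events not confirmed by the CEC, in the safety set, for the on-treatment and Up-to-Day-45 phases. Show it by event type and investigator diagnosis, with separate lines for ACS without MI, TIA, and hemoglobin fall or transfusion without overt bleeding. Place it alongside the SAE tables rather than merging it into them, because no section says that seriousness is recorded for suspected outcomes. Leave the waiver from expedited reporting and unblinding intact.
2. **Protocol 12.3.1 and 12.3.2.** Reconcile the rejected-event sentence with the hospitalization rule, so that a site knows which applies to a hospitalized event the CEC rejects. Reconcile the two sentences in 12.3.1 that apply to a death the CEC reclassifies as not VTE-related.

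The cost is one extra table from data already on the eCRF and in the adjudication records, plus a protocol wording change. No new data collection is needed for the table.
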